10.1. Explanation of Clinical Research Procedures to Subjects

10.2. Disclosure of Activities of Sponsor Representatives

Document No	TF.01.CIP.01	
Issue Date	01.05.2023	
Revision No	V.00	
Revision Date	120	

10.3.	Factors That May Compromise the Results of a Clinical Trial
11.	Data Management
12.	Amendments to the CIP
13.	Deviations from CIP
14.	Informed Consent Process

Revision Date	3225°	
Revision No	V.00	
Issue Date 01.05.202		
Document No	TF.01.CIP.01	

15. Adverse Events, Adverse Device Effects and Device Deficiencies

20.1. Definitions of Adverse Events and Adverse Device Effects

Adverse Event

An Adverse Event (AE) is any untoward clinical manifestation, including an unintended medical event, unintended illness or injury, or abnormal laboratory findings, occurring in subjects, users, or other persons in the context of a clinical trial, whether or not related to the trial.

This definition includes expected events as well as unexpected events.

This definition includes events occurring in the context of a clinical trial related to an investigational device, comparator, or related procedure.

Adverse Device Effect

An Adverse Device Effect (ADE) is any AE related to the use of an investigational medical device. This definition includes adverse events resulting from inadequate or inadequate use, placement, implantation, setup or operating instructions, or any malfunction of the investigational medical device. This definition includes any event resulting from an error in use or intentional misuse of the investigational medical device. This includes the 'comparator' if the comparator is a medical device.

20.2. Description of Device Deficiencies

Device Deficiency (DD) is any deficiency in the identity, quality, durability, reliability, safety, or performance of an investigational device, including malfunction, usage errors, or inadequacy in manufacturer-supplied information.

20.3. Definitions of Serious Adverse Events

Serious Adverse Event

A Serious Adverse Event (SAE) is any AE that results in any of the following: death, serious deterioration in the subject's health resulting in any of the following: life-threatening illness or injury, permanent impairment of a

Document No	TF.01.CIP.01
Issue Date	01.05.2023
Revision No	V.00
Revision Date	3 — 8

body structure or body function, hospitalization or extension of hospital stay, medical or surgical intervention to prevent life-threatening illness or injury or permanent impairment of body structure or body function, chronic disease, fetal distress, fetal death, or congenital physical or mental impairment or birth defect.

Serious Adverse Device Effect

A Serious Adverse Device Event (SADE) is an ADE that results in any of the characteristic consequences of a serious adverse event. SAEs related to procedures mandated by the clinical trial plan but not related to the use of the device will not be considered Serious Adverse Device Events.

Unanticipated Serious Adverse Device Effect

An unexpected SAE is an effect that is not identified in the current risk assessment by its nature, incidence, severity or consequence. Procedures related to the use of a device are addressed in the risk assessment, which makes it possible to determine whether the procedure for the SAEs is an Unexpected Serious Adverse Device Effect. SAEs related to procedures mandated by the clinical trial plan but not related to the use of the device will not be considered Serious Adverse Device Effects.

The clinical trial ends when the last subject completes the final follow-up. The sponsor will notify TITCK within 15 days following the end of the clinical trial and will send the clinical trial report, which includes an easy-tounderstand summary, within 1 year after the end of the clinical trial. The clinical trial will be registered in a public database before the start of the recruitment activities, and the content will be updated throughout the conduct of the clinical trial, and the results will be entered after the completion of the clinical trial. This clinical trial will be registered in a recognized public database for clinical trials (e.g. ClinicalTrials.gov, EU Clinical Trials Register) in order to ensure transparency and traceability of international clinical trials. This registration will include the main purpose of the trial, methodology, target population, outcome measures, and other relevant information. The findings and results of this trial will be published in a way that is accessible to the scientific community and the public. The trial results will be submitted for publication in peer-reviewed scientific journals and presented at national and international conferences. In addition, these results will be reported to the relevant health authorities and regulatory bodies. The results of the clinical trial will be published within the specified time frame after the completion of the study. A first draft report of the trial results will be prepared within 6-12 months after the completion of the study. The sponsor will play an active role in the analysis, reporting and publication of the trial results. The sponsor will also perform or have performed independent statistical analysis to ensure that the results are presented accurately and unbiased. Authorship criteria will be determined in accordance with the guidelines established by the International Committee of Medical Journal Editors (ICMJE). Authorship will be limited to investigators who have made a significant contribution to the study. This includes those who contributed to the study design, data collection, analysis, interpretation of the results and writing of the manuscript. Each author will confirm the accuracy of the results and approve the final version of the manuscript.

17. References

ANNEX 1.

STATISTICAL ANALYSIS PLAN

Analysis Population and Procedures

Analyses will be performed on a Per Protocol (PP) basis only. The PP analysis will include participants who completed the study per protocol and this population will accurately reflect the effectiveness and reliability of the software in diagnosing diabetic retinopathy, glaucoma and macular degeneration.

Baseline Data and Endpoints Descriptive Statistics

Baseline Data:

Baseline data includes the age and gender information of all patients participating in the clinical study. This data does not affect the results of the Retinow AI software. It will only be collected to obtain information about the age and gender distribution.

Endpoints Descriptive Statistics:

Endpoints are the sensitivity, specificity and accuracy rates of the Retinow Al software in diagnosing diabetic retinopathy, glaucoma and macular degeneration diseases. These rates show how well the software agrees with the diagnoses made by specialist physicians. Descriptive statistics are used to measure these rates. The definitions of these rates are provided below.

Sensitivity: The ability of the software to correctly identify individuals with the disease. High sensitivity reduces the probability that the software will miss signs of the disease. (True positive rate).

Specificity: The ability of the software to correctly identify healthy individuals. High specificity minimizes false positive results. (True negative rate).

Accuracy: It is defined as the percentage of correct results in all diagnoses of the software.

These descriptive statistics will be used to further evaluate the reliability, effectiveness, and usability of the Retinow Al software in clinical applications.

Analytical Procedures

The comparisons of the diagnosis of disease results in the clinical trial by the doctor and the Retinow Al software will be examined. The results will be analyzed with Cohen's Kappa analysis. The parameters to be analyzed are sensitivity, specificity and accuracy values. Sensitivity is defined as the accuracy between positive findings according to the clinical reference standard; It will be calculated as the ratio of eyes with positive findings according to the reference standard and positive results with the Retinow Al system. Specificity is defined as the accuracy between negative findings according to the clinical reference standard; It will be calculated as the ratio of eyes with negative findings according to the reference standard and negative results with the Retinow Al system. (Positive findings indicate being sick, negative findings indicate being healthy)

Statistical analyses will be performed using the Python programming language version 3.11.4 and the TensorFlow library version 2.10.0. In addition to these calculations, the Cohen's Kappa method will also be used for the analysis of the results. These analyses involve the use of the specified software versions and tools in the data processing and model building stages. This process aims to specify the relevant software and versions to ensure the reliability and framework of the research results. Considering the referenced cases as 'positive' and the non-referenced cases as 'negative', the sensitivity, specificity and accuracy scores are clinically significant measurements and will be calculated with 95% confidence intervals. For each disease, tables will be created to compare the sensitivity and specificity of the algorithm with the reference standard. The reference standard is defined as the majority decisions of the ratings of 3 expert ophthalmologists. The definitions of the positive and negative cases to be analyzed are given below.

Document No	TF.01.CIP.01
Issue Date	01.05.2023
Revision No	V.00
Revision Date	120

		Retinow AI				
		Disease	No Disease	Total	Kappa	p
Doctor	Disease	TP	FN			
	No Disease	FP	TN			
	Total					

Kappa Score: Cohen's Kappa score is a statistical method used to measure the agreement between two raters or observers. It shows how much the two parties agree, taking into account the probability of random agreement.

P: It is used in statistical tests to determine whether the results are significant. In a hypothesis test, it shows how much the data deviates from the expected distribution and expresses the probability that the results occurred randomly.

True Positive (TP): This refers to the situation where the software correctly diagnoses the disease. That is, it occurs when the software classifies an actual disease as a patient.

True Negative (TN): This refers to the situation where the software does not correctly diagnose the disease. That is, it occurs when the software classifies an actual healthy state as healthy.

False Positive (FP): This refers to the situation where the software incorrectly diagnoses the disease. That is, it occurs when the software classifies an actually healthy condition as sick.

False Negative (FN): This refers to the situation where the software does not incorrectly diagnose the disease. So it happens when the software classifies a real disease as healthy.

These terms are used to evaluate the accuracy and precision of software in classifying a disease or condition. True Positive and True Negative results represent conditions that were correctly diagnosed, while False Positive and False Negative results represent conditions that were misdiagnosed. Below is the calculation of sensitivity, specificity and accuracy values in our clinical study.

```
Sensitivity = TP/(TP + FN)
Specificity = TN/(TN + FP)
Accuracy = (TN + TP)/(TN + TP + FN + FP)
```

The passing criteria for the Retinow AI software in the clinical study will be based on its accuracy, sensitivity and specificity in diagnosing diabetic retinopathy, glaucoma and macular degeneration. The passing criteria were determined as 90% accuracy, 90% sensitivity and 90% specificity for all diseases. These threshold values are necessary for the software to be used as a reliable diagnostic tool in the clinical setting. In addition, it will be mandatory for the reliability of the study and the validity of the results to be kept below 10% of the possible technical errors and data loss rates. When these criteria are met, Retinow AI will be considered successful; otherwise, the software will not pass the study.

Sample Size

The required sample size for each study whose results will be analyzed with Cohen's Kappa analysis was calculated using Arifin's [82] calculation tool, which was developed based on the formula presented by Donner and Eliasziw [81].

Document No	TF.01.CIP.01
Issue Date	01.05.2023
Revision No	V.00
Revision Date	3 — 8

However, in order to provide additional safety margin against possible data loss and participant losses at each stage of the study, it was planned to conduct the study with 305 people for each disease (diabetic retinopathy, glaucoma and macular degeneration). In this way, the reliability of the data and the statistical validity of the results will be preserved. The sample size calculations made in the calculation tool are given below.

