- 4. Fundus Photography: In this study, no invasive procedure will be applied to the patient, and the retinal photography will be taken by the camera operator with a special non-mydriatic digital camera called a fundus camera. In some patients diagnosed with Retinow AI, pharmacological dilatation (mydriasis) using a dilatation solution may be required to obtain a fundus image of sufficient quality. The dilatation procedure will be performed only by healthcare personnel (general practitioners, nurses, etc.) who are competent and trained in this regard.
- 5. Recording of Images: Right and left fundus images of each participant will be taken and these images will be recorded by the responsible researcher. The principal investigator will download the images via the hospital's PACS system.
- 6. Analysis of Images: Fundus photographs will be analyzed by the Retinow AI device. Then, they will be analyzed by expert ophthalmologists for gold standard evaluation.

Revision Date	920	
Revision No	01.05.2023 V.00	
Issue Date		
Document No	TF.01.CIP.01	

8. Gold Standard Assessment: The gold standard assessment results performed by specialist doctors will be used to determine the sensitivity and specificity of the Retinow Al device.

Al Analysis: Retinow Al software will analyze the collected images within 24 hours of image acquisition. This rapid analysis will allow for a near real-time comparison with expert diagnoses.

Clinical data will be fed into Retinow Al software and the success metrics (Accuracy, Sensitivity, Specifity) will be evaluated. Diagnostic labels provided by Retinow Al software will be compared with labels provided by expert ophthalmologists. Performance metrics of accuracy, sensitivity and specificity will be calculated.

The clinical study will be completed when the predicted number of data is reached

9. Subjects

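### Sensitivity and specificity are counted per eye and both eyes are imaged, but no method allows for correlation between a participant's two eyes

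*Combined protocol and SAP*

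**What the plan says.** Annex 1, Analytical Procedures, defines sensitivity by eyes: "It will be calculated as the ratio of eyes with positive findings according to the reference standard and positive results" with the software. Specificity follows the same pattern: "It will be calculated as the ratio of eyes with negative findings according to the reference standard and negative results". Sensitivity, specificity and accuracy "will be calculated with 95% confidence intervals". On agreement the section says "The results will be analyzed with Cohen's Kappa analysis", and its 2x2 table of TP, FN, FP and TN carries columns for kappa and p. The three rates are then given as plain proportions from those cells.

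Protocol section 8, step 5 of the study procedure, says: "Right and left fundus images of each participant will be taken and these images will be recorded by the responsible researcher".

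Two other passages bear on the unit. Annex 1, Endpoints Descriptive Statistics, words sensitivity per person ("The ability of the software to correctly identify individuals with the disease") and accuracy without a unit ("It is defined as the percentage of correct results in all diagnoses of the software"). The success rule reads: "The passing criteria were determined as 90% accuracy, 90% sensitivity and 90% specificity for all diseases". The Sample Size section counts people, 305 per disease.

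**The concern.** Two eyes of one person share age, systemic disease and imaging session, and often the diagnosis. An image-reading algorithm that errs on one eye may well be more likely to err on the other. The second eye then adds less than a full independent observation, and an ordinary binomial or kappa formula applied to pooled eyes counts it as one. The visible SAP names no interval method, clustered variance, one-eye rule or rule for combining two eyes into one result. Its single 2x2 table and plain proportions lead naturally to pooled-eye formulas.

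The 95% intervals are the planned statement of precision for the primary endpoints, and the protocol commits to publishing the results and reporting them to regulators. Under positive correlation, ordinary intervals would claim more certainty than the data hold.

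The unit also differs between the two parts of Annex 1. A participant-level reading would need a two-eye rule, which the plan does not contain.

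**Working it through.** **The plan's own figure.** 3 x 305 = 915 matches the stated number of participants. The 305 cannot be reproduced, because the kappa inputs are not visible. No sample size shortfall is claimed.

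**Inputs from the documents.** The eye is the unit, there are two eyes per participant, the confidence level is 95%, the target rate is p = 0.90, and there are 305 people per disease.

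**Assumptions, not in the documents.** The inter-eye error correlation rho is 0.3 to 0.8, with lower values shown below. A row of the table holds 153, 305 or 610 people. The 610 case applies only if participants with the other diseases count as negatives, which fits less well with the SAP's remark that negative means healthy.

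**Interval width.** With m eyes in a row, some forming pairs from one person:

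Variance = p(1-p)(m + 2 x pairs x rho)/m²

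If everyone contributes both eyes, the variance is multiplied by 1 + rho. For 305 people (610 eyes) the ordinary half-width is 1.96 x sqrt(0.09/610) = 2.38 points. At rho 0.5 it becomes 2.38 x sqrt(1.5) = 2.92.

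| People (eyes) | Ordinary | rho 0.3 | rho 0.5 | rho 0.8 |
|---|---|---|---|---|
| 153 (306) | 3.36 | 3.83 | 4.12 | 4.51 |
| 305 (610) | 2.38 | 2.71 | 2.92 | 3.19 |
| 610 (1,220) | 1.68 | 1.92 | 2.06 | 2.26 |

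**Coverage of the ordinary interval.** Coverage = 2Φ(1.96/sqrt(DE)) - 1, where DE is the design effect.

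- Both eyes in the row, DE = 1 + rho: 91.4%, 89.0% and 85.6% at rho 0.3, 0.5 and 0.8. At rho 0.1 and 0.2 it is 93.8% and 92.6%.
- Half the people contributing one eye (610 people, 915 eyes, 305 pairs), DE = 1 + 610 x rho/915 = 1.20, 1.33 and 1.53: 92.6%, 91.0% and 88.7%.
- One eye per person, or rho = 0: no loss.

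A simulation of 40,000 runs (305 people, both eyes, p = 0.90) gave 92.0%, 90.0% and 86.4% at rho 0.3, 0.5 and 0.8, and 95.3% at rho 0. A participant-level cluster variance gave 94.2% to 94.6%.

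**Kappa.** The kappa table uses the same TP, FN, FP and TN cells as the eye-level rates, so it is taken as per eye. Assume 152 diseased and 153 healthy people, both eyes with the same status, and sensitivity and specificity both 90%. Observed agreement is 0.90 and chance agreement about 0.50, so kappa = (0.90 - 0.50)/(1 - 0.50) = 0.80. In 3,000 simulated runs the ordinary standard error was 0.024, against a true 0.028, 0.030 and 0.033 at rho 0.3, 0.5 and 0.8. Coverage was 92.8%, 89.9% and 86.1%. A cluster-robust error restored 94.3% to 94.9%.

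The null value for the kappa p-value is not stated. Against zero, with no true agreement and 305 people, the ordinary 5% test rejected in 9.0%, 11.0% and 14.7% of runs (5.4% at rho 0).

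**If the participant were the unit.** Purely as illustration, suppose a person is called positive when either eye is, and eye-level specificity is 92%. Participant specificity is then 0.92² + rho x 0.92 x 0.08 = 0.8464 + 0.0736 x rho, which is 86.8%, 88.3% and 90.5% at rho 0.3, 0.5 and 0.8. Below about rho 0.73 the same data pass 90% per eye and fail it per participant.

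**The case against.** The strongest reply is that no planned decision changes. The success rule sets 90% thresholds and mentions no confidence bound, and a kappa near 0.8 is far from zero whichever standard error is used. At 305 people the interval differs by only 0.3 to 0.8 of a point. This stands, and it limits the point to reported precision.

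A second reply is that the SAP omits a method and does not prescribe a wrong one. Ordinary formulas are an assumption, and the relevant text may be out of view: step 7 of the procedure list, several sections and the sample size output cannot be seen. The claim is therefore conditional. But the SAP's analysis section, where such a rule belongs, reads continuously and has none. It specifies software versions but no interval method.

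Third, rho is unknown and could be below 0.3, where the loss is small, and eyes of discordant disease status fall in different rows for sensitivity and specificity. The kappa simulations did not cover discordant eyes. Both caveats affect the size of the error, not its direction under positive correlation.

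Finally, if the participant is the intended unit, the clustering point disappears. The eye is nevertheless what Analytical Procedures states, and the participant reading needs a two-eye rule that is also absent.

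**Conclusion.** The concern holds and should be fixed before analysis. The plan counts eyes, images two per person, asks for 95% intervals and a kappa p-value, and shows no provision for within-person correlation. With ordinary formulas, rho of 0.3 to 0.8 and both eyes in the row, intervals are too narrow by a factor of sqrt(1 + rho), 1.14 to 1.34, and nominal 95% coverage is about 91% to 86%. The loss is smaller if rho is lower or many people contribute one eye, and zero with one eye each. Confidence is medium, because rho, the row denominators and some of the text are not available. Interval width does not affect pass or fail as the rule is written. The choice between eye and participant could, through a two-eye rule not yet written.

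**What to change.** - Keep the eye-level point estimates of Analytical Procedures.
- Compute the 95% intervals for sensitivity, specificity, accuracy and kappa, and the kappa p-value, with the participant as cluster. A participant-level bootstrap, GEE or a cluster-robust variance would each serve. Name one in the SAP.
- Align the descriptive definitions of sensitivity and specificity, and the definition of accuracy, so that the eye is the unit for the 90% criteria.
- If the sponsor intends the participant as the unit instead, write down how two eyes become one result, for the software and for the reference standard, before the labels are compared.
- If a rule already exists in text that is not public, a cross-reference from Annex 1 is enough.

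The cost is SAP wording and a few lines of Python, with no new data. Intervals become about 14% to 34% wider for rho 0.3 to 0.8 when both eyes are in the row, and less when some people contribute one eye.

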4.1. Summary Description of The Investigational Device

Retinow Al is a software, a medical device that aims to solve a global problem that eliminates the risk of vision loss, especially in developed countries. Retinow Al provides rapid screening and triage without the need for a trained expert to evaluate digital retina (fundus) images. Digital retina images pass through the Retinow Al cloud system and are interpreted with the help of artificial intelligence, helping to detect diabetic retinopathy, glaucoma and macular degeneration diseases.

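### Sensitivity and specificity are defined for individuals but calculated per eye, and the 90% pass marks name no unit

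*Combined protocol and SAP*

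**What the plan says.** Annex 1, under Endpoints Descriptive Statistics, describes sensitivity as "The ability of the software to correctly identify individuals with the disease" and specificity as "The ability of the software to correctly identify healthy individuals". Both are statements about people.

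Under Analytical Procedures in the same annex, the calculation is by eye. For sensitivity: "It will be calculated as the ratio of eyes with positive findings according to the reference standard and positive results" from the software. For specificity: "It will be calculated as the ratio of eyes with negative findings according to the reference standard and negative results". Results are split by disease: "For each disease, tables will be created to compare the sensitivity and specificity of the algorithm with the reference standard".

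The success rule at the end of that section reads: "The passing criteria were determined as 90% accuracy, 90% sensitivity and 90% specificity for all diseases". It names neither eyes nor people. Missing the criteria means that the software does not pass.

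Three other places bear on the unit:
- Section 8, step 5, has right and left images taken for every participant.
- The Sample Size part of Annex 1 counts people: 305 per disease.
- Section 4.1 says the device "provides rapid screening and triage without the need for a trained expert to evaluate digital retina (fundus) images", and the study objectives in section 3 include screening healthy individuals.

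The readable text has no rule for turning two eye results into one result per person, and none for combining the three disease results.

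**The concern.** The same two rates carry a person-level definition and an eye-level formula, and they decide whether the device passes. With two eyes imaged per participant, the two versions give different point estimates. This is separate from interval width: an interval that allowed for the pairing of eyes would still be centred on the eye-level figure.

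If the plan is followed as written, an eye-level result can be reported under a definition that speaks of the ability to "correctly identify healthy individuals". A reader would take 90% specificity to mean that nine in ten healthy people are cleared, which the readable plan never estimates. The unit can also decide the outcome, because some eye-level results pass by eye and fail by person.

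**Working it through.** **Inputs.** Pass mark s = 0.90 (Annex 1, Analytical Procedures). Two eyes per participant (section 8, step 5). Three diseases, tabulated separately (Annex 1). The correlations between eyes and between diseases are not in the documents, so they are assumed and shown as ranges.

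**1. The plan's own figure.** 3 × 305 = 915, which agrees with the total in section 3. The 305 itself cannot be reproduced, because the calculator inputs are not in the readable text. Nothing below depends on it.

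**2. One disease, two eyes.** Assume that a person is negative only if both eyes are negative, and that the table's negatives are healthy participants' eyes. With between-eye correlation φ of the calls, P(both negative) = s² + φ·s(1 − s).
- φ = 0: 0.90² = 0.81
- φ = 0.5: 0.81 + 0.5 × 0.09 = 0.855
- φ = 1: 0.81 + 0.09 = 0.90
- Lowest possible, with false positives never in both eyes of one person: 1 − 2 × 0.10 = 0.80

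As a count, take 305 healthy people (610 eyes) with 61 false-positive eyes, all in different people. Eye-level specificity is 549/610 = 90.0%; person-level specificity is 244/305 = 80.0%.

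To clear 90% of healthy people under independence, eye-level specificity would have to be √0.90 = 94.9%. Under that assumption, eye-level results from 90% up to 94.9% pass by eye and fail by person.

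**3. Three diseases, two eyes.** This further assumes a separate call for each disease and that any positive call flags the person, giving six calls.
- Bounds under any dependence: 1 − 6 × 0.10 = 0.40 to 0.90
- Independence: 0.90⁶ = 0.531
- Exchangeable Gaussian latent scores with correlation ρ, where P = ∫ Φ((z₀.₉₀ − √ρ·u)/√(1 − ρ))⁶ φ(u) du and φ(u) is here the standard normal density:

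| ρ | Share of healthy people with all six calls negative |
|---|---|
| 0.3 | 62.0% |
| 0.5 | 67.9% |
| 0.7 | 74.2% |
| 0.9 | 81.8% |

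**4. Sensitivity moves the other way.** Take disease in both eyes, 90% sensitivity per eye, and a person counted positive if either eye is called. Person-level sensitivity is 1 − 0.10² = 0.99 if misses are independent, 1 − (0.01 + 0.5 × 0.09) = 0.945 at correlation 0.5, and 0.90 if misses always coincide.

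**5. Who the negatives are.** Steps 2 and 3 need the negatives to be healthy participants' eyes. The plan does not say whether fellow eyes, or eyes with another disease, also count. An assumed mix shows why this matters. If one third of negatives are healthy eyes with 100% specificity and two thirds are other-disease eyes with 85%, the table reads 1/3 × 1.00 + 2/3 × 0.85 = 0.90 while every healthy person is cleared.

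**The case against.** The person-level sentences can be read as a plain-language glossary. The only sentences that say how the rates will be calculated refer to eyes, so the eye is arguably the operative unit. Eye-level performance is also relevant here: the primary objective concerns diagnosis from fundus photographs, and section 4.2 describes decision support for physicians. This stands in part. A reader might infer that the trial answers the wrong question, but the documents do not go that far. They give two units and do not say which one the pass mark uses.

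A reader might also infer that a pass can hide far fewer than 90% of healthy people being cleared, with 53% as the expected figure. The documents do not support that as the main conclusion. The eye-versus-person conflict costs at most 10 percentage points for one disease. The larger shortfall needs a six-call composite that the plan does not promise, and separate binary calls that it does not describe; section 8 speaks only of diagnostic labels. The 53% also needs independence, which is doubtful for images from one person read by one algorithm.

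Nor is eye-level specificity, as a general fact, an upper bound on the share of healthy people cleared. That holds only if the negatives are healthy participants' eyes; step 5 of the working gives a counterexample.

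Finally, parts of the document are missing from the readable text, so the absence of a per-person rule is established only for what can be read.

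**Conclusion.** The inconsistency is explicit and affects the decision endpoint: individuals in the definition, eyes in the formula, no unit in the pass mark, people in the sample size. For one disease at 90% per eye, between 80% and 90% of healthy people are cleared, given the both-eyes-negative rule and healthy participants' eyes as the negatives. Clearance across all three diseases is not estimated in the readable plan. Its possible range is 40% to 90%, and no single value in that range should be presented as expected. Sensitivity has the same conflict of unit, but there an any-eye rule favours the device. The text needs to change whichever unit the sponsor intends.

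**What to change.** In Annex 1:

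1. Use one stated unit in the endpoint definitions, the formulas and the passing criteria. The participant is the natural choice, since it matches the definitions and the sample size.
2. Define the person-level result for each disease, in the same way for the software and for the three-expert majority reference.
3. State whether fellow eyes and eyes with another disease count as negatives.
4. Report the share of reference-healthy participants with no disease called in either eye. Base any statement about healthy individuals on that figure.
5. Keep the eye-level tables as secondary, so that a call in the wrong eye stays visible, with intervals that allow for two eyes per person.

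The cost is SAP wording and one additional table, from images and ratings already planned. There are two downsides. The specificity figure will be less favourable, and an any-eye rule makes the sensitivity mark easier to pass (90% per eye becomes 90% to 99% per person in bilateral disease, from coinciding to independent misses). Both levels should therefore be shown side by side.

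If the sponsor prefers to keep the eye as the unit, the definitions must be reworded to say so, and a pass must not be described as performance in healthy individuals.
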